#### **8.1.6. Unscheduled Visits**

If a subject returns to the clinical site before their next scheduled visit for an assessment of an AEs or at the request of the physician, all safety assessments should be performed and any additional assessments as deemed medically necessary by the physician.

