2.2.5. Safety Endpoints

- Incidence and severity of ocular and systemic treatment-emergent adverse events.
- Incidence of ADA directed against pegcetacoplan peptide or PEG.
- Incidence of new active CNV in the study eye.
- Incidence of new onset of subclinical CNV in the study eye.
- Incidence of subjects who lost letters based on NL-BCVA categories (≥ 15 , $\geq 15 - < 30$, ≥ 30 ETDRS letters).
- Change/shift from baseline in clinical labs and incidence of abnormal lab values.
- Change from baseline in vital signs and incidence of abnormal vital sign results.
- Shift from baseline in ocular examination assessments including slit-lamp examination and indirect ophthalmoscopy.
- Change from baseline in Intra Ocular Pressure (IOP) and incidence of IOP above specified thresholds.
- Change/shift from baseline in ocular imaging assessments (including specular microscopy; select sites).

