7.6. NL-BCVA

The number and percentage of subjects who lost letters compared with baseline at each visit based on NL-BCVA in the study and fellow eye will be presented. The three categories are ≥ 15 , $\geq 15 - < 30$ and ≥ 30 ETDRS letters.

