13.4. Definition of Visit Windows

All assessments occurring on or before the first date of dosing (Analysis Study Day (ADY) ≤ 1) will be assigned to the Baseline analysis visit window.

Unless otherwise specified, the actual scheduled nominal post-baseline visit will be used for over time summaries. Post-baseline unscheduled visits and early termination visits will be mapped to a scheduled visit and will only be used in the analysis if the nominal scheduled visit result is missing, [Table 5](#) and [Table 6](#) presents the analysis visit window mapping for unscheduled and early term visits. In the case that multiple unscheduled or early termination visits are in the same analysis window, the one closest to the target date will be used. In the event that windowed visit is mapped to an illogical sequence of visits when considering nearby scheduled visits

(i.e., windowed visit is higher than the subsequent visit or lower than the preceding visit), the windowed visit will be set to the logical scheduled visit.

Table 5: Post-Baseline Analysis Visit Window for Unscheduled and Early Termination Visits: Monthly Regimen

Analysis Visit	Target Study Day	Analysis Window (days)
Day 7	7	2 to 15
Month 1	30	16 to 45
Month 2	60	46 to 75
Month 3	90	76 to 105
Month 4	120	106 to 135
Month 5	150	136 to 165
Month 6	180	166 to 195
Month 7	210	196 to 225
Month 8	240	226 to 255
Month 9	270	256 to 285
Month 10	300	286 to 315
Month 11	330	316 to 345
Month 12	360	346 to 375
Month 13	390	376 to 405
Month 14	420	406 to 435
Month 15	450	436 to 465
Month 16	480	466 to 495
Month 17	510	496 to 525
Month 18	540	526 to 555
Month 19	570	556 to 585
Month 20	600	586 to 615
Month 21	630	616 to 645
Month 22	660	646 to 675
Month 23	690	676 to 705
Month 24	720	706 to EOS

Table 6: Post-Baseline Analysis Visit Window for Unscheduled and Early Termination Visits: Every Other Month Regimen

Analysis Visit	Target Study Day	Analysis Window (days)
Day 7	7	2 to 15
Month 1	30	16 to 45
Month 2	60	46 to 75
Month 3	90	76 to 105
Month 4	120	106 to 135
Month 5	150	136 to 165
Month 6	180	166 to 195
Month 7	210	196 to 225
Month 8	240	226 to 255
Month 9	270	256 to 285
Month 10	300	286 to 315
Month 11	330	316 to 345
Month 12	360	346 to 375
Month 14	420	376 to 450
Month 16	480	451 to 510
Month 18	540	511 to 570
Month 20	600	571 to 630
Month 22	660	631 to 690
Month 24	720	690 to EOS

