13.6. Repeated or Unscheduled Assessments of Safety Parameters

If a subject has repeated assessments before the start of investigational product, then the results from the final assessment made prior to the start of investigational product will be used as baseline. If end-of-study assessments are repeated or unscheduled, the last post-baseline assessment will be used as the end of study assessment for generating descriptive statistics. However, all post-baseline assessments will be used for PCS value determination and all assessments will be presented in the data listings.

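### The letter-loss safety endpoint is named as an incidence but tabulated only visit by visit, so no subject-level cumulative figure is produced and a short-lived loss between scheduled visits can be absent from the table

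*SAP*

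**What the plan says.** SAP 2.2.5 gives the safety endpoint as "Incidence of subjects who lost letters based on NL-BCVA categories", with the categories at least 15, 15 to under 30, and at least 30 ETDRS letters. SAP 7.6 is the safety analysis of that endpoint: "The number and percentage of subjects who lost letters compared with baseline at each visit based on NL-BCVA in the study and fellow eye". It has no row for loss at any time, for the worst value, or cumulatively.

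SAP 13.4 decides which scores feed a by-visit table. Unless otherwise specified, "the actual scheduled nominal post-baseline visit will be used for over time summaries". Unscheduled and early-termination results are mapped to a month and "will only be used in the analysis if the nominal scheduled visit result is missing". If several such results fall in one window, "the one closest to the target date will be used", so the choice does not depend on which is worst.

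SAP 13.6 is wider for one purpose: "all post-baseline assessments will be used for PCS value determination and all assessments will be presented in the data listings". PCS criteria exist only for laboratory tests (SAP Table 3) and vital signs (SAP Table 4), so this does not reach acuity. The last observed value in SAP 7 is the last assessment, not the lowest.

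Protocol 8.1.6 covers visits made for an adverse event or at the physician's request: "all safety assessments should be performed and any additional assessments as deemed medically necessary by the physician". It does not name acuity, but SAP 7 and Protocol 12.8.3 both class visual acuity among the ocular safety assessments.

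**The concern.** Two things are at stake. First, the SAP promises an incidence and delivers a series of prevalences. A reader of the report who wants to know how many subjects per arm ever lost 15 or 30 letters will not find that number.

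Second, the by-visit table is built to show where acuity stands at scheduled visits. A loss that begins soon after an injection and recovers before the next scheduled test is the pattern such a table is least able to show. Protocol 4.2 gives some reason to care: it mentions transient moderate and severe intraocular inflammation in recent studies of intravitreal pegcetacoplan, though only with product from a single manufacturer and without mentioning letter loss.

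**Working it through.** The documents state no rate, sample size or power for letter loss, so there is no figure of the plan to reproduce. The check is mainly a tracing of rules.

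**1. By-visit percentages do not determine an incidence.** If p_k is the proportion with loss at visit k, and every subject contributes at every visit, the proportion P with loss at one or more visits is only bounded: max(p_k) ≤ P ≤ min(1, Σp_k). One subject may count at many visits, or different subjects at different visits.

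**2. Number and spacing of scheduled NL-BCVA tests (Protocol 8.1.4 and Appendices A to D).**
- Monthly arms: 24 post-baseline visits (Months 1 to 24).
- EOM arms: 12 in year 1 plus 6 in year 2 (Months 14, 16, 18, 20, 22, 24) = 18. These 18 are the visits common to all arms.
- Gap from an injection to the next scheduled test: about 30 days in the monthly arms and in EOM year 1, and about 60 days for EOM injections from Month 12 on.
- The check within 5 minutes of injection (Protocol 9.15) is of gross vision, not letters.

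**3. Where an unscheduled score goes.** Protocol 9.10 puts acuity testing before dilation or contact with the eye, so the score at a dosing visit is normally taken before the injection. Take a monthly subject injected on Day 90 who returns on Day 95 with acute loss. In SAP Table 5 the Month 3 window is Days 76 to 105, so Day 95 maps back to Month 3, which already holds the pre-injection score. The Day 95 score is not used. For an on-target injection this lasts 105 − 90 = 15 days. In EOM year 2, the SAP Table 6 window for Month 16 is Days 451 to 510, so it lasts 510 − 480 = 30 days. A later score maps to the next visit and is used only if that visit's scheduled score is missing. The Day 1 injection is an exception: no acuity test is scheduled in the Day 7 window, so an unscheduled score has nothing to displace it there.

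**4. How the SAP treats comparable harms.** SAP 7.5 summarises IOP threshold crossings by timepoint and over the whole study. SAP 7.7 gives new CNV on angiography a Kaplan-Meier cumulative incidence, and counts subjects with one or more suspected CNV cases. Letter loss gets neither form.

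**5. Illustration only.** Assume that 0.25% of injections are followed by a loss of at least 15 letters (the documents give no rate), with onset 0 to 5 days after injection and visits spread over the protocol windows. The share ever affected over 24 months is 1 − (1 − 0.0025)^24 = 5.8% for PM and 1 − (1 − 0.0025)^12 = 3.0% for PEOM. Simulation then gives:

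| Duration of loss | PM: seen at any scheduled visit | PM: highest single visit | PEOM: seen at any scheduled visit | PEOM: highest single visit |
|---|---|---|---|---|
| 7 days | 0.00% | 0.00% | 0.00% | 0.00% |
| 14 days | 0.11% | 0.01% | 0.02% | 0.01% |
| 30 days | 3.85% | 0.19% | 0.94% | 0.18% |
| 60 days | 5.84% | 0.46% | 2.31% | 0.28% |

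In the 30-day PM case, a by-visit table peaking at 0.19% fits any-visit shares from 0.19% up to 24 × 0.19% = 4.56%. The simulated value is 3.85%, and 5.8% are ever affected. The percentages scale with the assumed rate. What does not depend on it is that a loss of a week or so falls wholly between scheduled visits.

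**The case against.** The strongest reply is that acute harm is captured mainly as adverse events, not through this table, and much of that reply stands. Protocol 11.7 exempts only normal progression of the disease from reporting. SAP 7.5 requires relevant post-baseline findings on examination to be reported as adverse events, and Protocol 7.5.3 makes endophthalmitis an SAE. The early follow-up calls ask about decreased vision. SAP 7.1 tabulates ocular events by eye, severity and seriousness, with per-injection rates for endophthalmitis and intraocular inflammation. SAP 7.1.1 shows acuity before and at exudation. SAP 6.3.2.3 lists all NL-BCVA data, and the DMC sees unmasked data about every 6 months. A reader might infer that such a loss disappears from the report, or that unscheduled scores are always discarded. The documents support neither: a score is used when the scheduled one is missing and can be the last observed value. But none of these outputs gives the number of subjects per arm who ever lost 15 or 30 letters.

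The second reply is that scheduled visits are the fair basis for comparison. This also stands, and it shapes the fix. Unscheduled visits are prompted by events. In Phase 2, new exudation occurred in 25 of 165 treated subjects (15%) against 1 of 81 on sham (1%) (Protocol 4.1.4), so active arms may have more such visits and more chances to cross a noisy threshold. That is a reason to show two rows, not to omit the cumulative one.

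**Conclusion.** The mismatch holds on the text alone: SAP 2.2.5 names an incidence, SAP 7.6 produces by-visit counts, and SAP 13.4 keeps an unscheduled score out of those counts whenever the scheduled score exists. It affects one descriptive safety table and no efficacy test. That acuity is measured at unscheduled visits is a well-supported inference, since Protocol 8.1.6 does not name it.

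Two stronger readings are not supported. One is that the omission demonstrably favours pegcetacoplan. Sham puts no needle or drug into the eye, so loss caused by injection would fall on the active arms. But the endpoint counts loss from any cause, GA itself reduces acuity, and no document says how often acute loss occurs or how fast it recovers. The other is a count of missed subjects. One can write 200 × 24 = 4,800 PM injections, assume 0.05% to 0.2% with acute loss (2.4 to 9.6 events), assume that half recover before the next visit, and reach roughly 1 to 5 subjects. Both fractions are assumptions, and the sum also takes every planned injection as given and every event as a different subject. It illustrates scale and estimates nothing.

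**What to change.** Add to SAP 7.6, for the study eye and the fellow eye, through Month 12 and through Month 24, the number and percentage of subjects with a loss of at least 15 letters, 15 to under 30 letters (by worst value), and at least 30 letters:

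- **(a)** at any scheduled visit common to all arms (Months 1 to 12, 14, 16, 18, 20, 22, 24). Say whether SAP 13.4 fallback scores count here; leaving them out keeps event-triggered scores out of the comparison.
- **(b)** at any post-baseline assessment, including unscheduled and early-termination visits, with scheduled year-2 visits limited to the common months. State that the SAP 13.4 only-if-missing rule does not apply to this row.

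Label (a) as the comparative row and (b) as the capture row. Note under the table that the first category contains the other two, and give the number of contributing assessments per subject by arm. The last item matters because the COVID-19 provisions (Protocol Appendix K) let EOM subjects skip non-dosing visits, so year-1 visits may not be equally attended. A row for sustained loss is optional.

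The cost is one SAP paragraph and a few table rows, from data already collected. The downside should be stated: (b) includes test-retest noise and unequal ascertainment, so a difference between arms in (b) that is absent from (a) should not be read as a treatment effect without looking at the cases.

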7.7. Other Ophthalmology Imaging Assessments

Unless otherwise stated, ocular imaging data collected will be listed by treatment group and overall for the Safety set. The summary will be performed separately by study eye and by fellow eye. The ophthalmology imaging assessments performed in this study include the following:

- Digital Color Fundus Photographs (DCFP)
 - Shift from baseline in the presence/absence of hemorrhage at each visit
- FA
 - The following analyses will be performed in all study eyes and in non-study eyes without a history of CNV at baseline (in medical history) in the corresponding eye.
 - Incidence of new CNV. This will be summarized as the cumulative number of CNV events by each visit and the cumulative incidence by that visit based on Kaplan Meier methods.
 - Incidence of new CNV by type (classic, occult, classic & occult, disciform scar) at first emergence will be summarized at each visit for the cumulative number of events.
 - Total CNV size (diameter) at first emergence will be summarized at each visit for the cumulative number of events.
- SD-OCT
 - Descriptive statistics on central subfield thickness at each visit
 - Plot of the mean change from baseline in central subfield thickness in the study eye \pm the standard error over time by treatment group.
 - Descriptive statistics on central (center point) retinal thickness at each visit
 - Shift from baseline in the presence/absence of subretinal fluid at each visit
 - Shift from baseline in the presence/absence of cystoid spaces at each visit
- Specular Microscopy

- Endothelial Cell Count is assessed using specular microscopy, and the change from baseline in cell density (cells/mm²) as well as the change from baseline in average cell-size will be summarized with descriptive statistics.
- OCT-A
 - Incidence of subclinical CNV (referred to as MNV in the datasets) determined by OCT-A in eyes without previous CNV reported in the medical history or as an adverse event in the corresponding eye at each visit.

In addition, the following summary of suspected and reading-center confirmed CNV cases will be presented by treatment group. This will be presented separately for the study eye only.

- The number and percentage of subjects with an Exudative AMD TEAE on or before Month 12 (or Month 24 if the final analysis)
- The number and percentage of subjects with at least one suspected new onset CNV case submitted to the reading center by the Investigator post-baseline through Month 12 (or Month 24 if the final analysis)
- The number and percentage of subjects with a reading-center confirmed new onset CNV case (out of the suspected CNV cases submitted by the Investigator) post-baseline through Month 12 (or Month 24 if the final analysis). Reading-center confirmed CNV case is identified as either:
 - Presence of CNV on FA (Type = classic, occult, classic & occult, disciform scar) OR
 - Presence of CNV thickness on SD-OCT
- The number and percentage of subjects with a reading-center confirmed new onset CNV case (out of the suspected CNV cases submitted by the Investigator) post-baseline through Month 12 (or Month 24 if the final analysis) and also reported as an Exudative AMD TEAE.
- The number and percentage of subjects with a reading-center confirmed new onset CNV case (out of the suspected CNV cases submitted by the Investigator) post-baseline through Month 12 (or Month 24 if the final analysis) without an Exudative AMD TEAE ever reported.
- The number and percentage of subjects with at least one suspected CNV case, confirmed by the reading-center but previously reported as an Exudative AMD TEAE.
- The number and percentage of subjects with at least one suspected CNV case, not confirmed by the reading-center but still reported as an Exudative AMD TEAE.
- The number and percentage of subjects with a reading-center finding of presence of new-onset CNV (defined in the same way as a confirmed new onset CNV case) without any other submission to the reading center of a suspected case post-baseline through Month 12 (or Month 24 if the final analysis) and also reported as an Exudative AMD TEAE on or before Month 12 (or Month 24 if the final analysis)

- The number and percentage of subjects with a reading-center finding of presence of new-onset CNV (defined in the same way as a confirmed new onset CNV case) without any other submission to the reading center of a suspected case post-baseline through Month 12 (or Month 24 if the final analysis) and no report of an Exudative AMD TEAE.
- The number and percentage of subjects with Exudative AMD TEAE and without a suspected case submitted to the reading center as well as without a reading center finding of new-onset CNV (defined in the same way as a confirmed new onset CNV case).

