### 6.1.2. Exclusion Criteria

Ocular specific exclusion criteria apply to the **study eye** only, unless otherwise specified.

1. GA secondary to a condition other than AMD such as Stargardt disease, cone rod dystrophy, or toxic maculopathies like plaquenil maculopathy in either eye.
2. Spherical equivalent of the refractive error demonstrating >6 diopters of myopia or an axial length >26 mm.
3. Any history or active CNV, associated with AMD or any other cause, including any evidence of RPE tears or evidence of neovascularization anywhere based on SD-OCT imaging and/or FA as assessed by the reading center.
4. Presence of an active ocular disease that in the opinion of the investigator compromises or confounds visual function, including but not limited to, uveitis, other macular diseases (eg, clinically significant epiretinal membrane, full thickness macular hole or uncontrolled glaucoma/ocular hypertension). Benign conditions in the opinion of the investigator such as peripheral retina dystrophy are not exclusionary.
5. Intraocular surgery (including lens replacement surgery) within 3 months prior to randomization.
6. History of laser therapy in the macular region.
7. Aphakia or absence of the posterior capsule. Note: Yttrium aluminum garnet laser posterior capsulotomy for posterior capsule opacification done at least 60 days prior to screening is not exclusionary.
8. Any ocular condition other than GA secondary to AMD that may require surgery or medical intervention during the study period or, in the opinion of the investigator, could compromise visual function during the study period.
9. Any contraindication to IVT injection including current ocular or periocular infection.
10. History of prior IVT injection.
11. Prior participation in another interventional clinical study for IVT therapies in either eye (including subjects receiving sham).
12. Prior participation in another interventional clinical study for GA in either eye including investigational oral medication and placebo.
13. Participation in any systemic experimental treatment or any other systemic investigational new drug including within 6 weeks or 5 half-lives of the active ingredient (whichever is longer) prior to the start of study treatment. Note: clinical trials solely involving observation, over-the-counter vitamins, supplements, or diets are not exclusionary.

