### **8.1.2. Randomization/Initial Treatment—Day 1—Within 28 Days of Screening**

#### **8.1.2.1. Visit 2—All Groups**

At this visit, all inclusion/exclusion criteria should be reviewed prior to randomization and dosing, including the determination of eligibility by the reading center. Subjects will be randomized using the interactive web response system. A complete ophthalmic exam including

slitlamp exam of the cornea, iris, anterior chamber, lens, and aqueous reaction (cells and flare), dilated fundus exam of the vitreous and retina, and IOP measurement will be performed and imaging collected as per the Visit Schedule.

All assessments should be performed on the same day. All study visits should be scheduled and projected based on the Day 1 visit date with the exception of Visit 2a which should be based on the Day 1 dose date.

Blood should be drawn for PK and complement profiling (select sites only) and anti-pegcetacoplan antibodies.

Prior to dilating the eyes, all functional tests should be performed (NL-BCVA, LL-BCVA, and MNREAD or Radner Reading Charts [in select countries]). Subjects at select sites will be trained on how to use the home-based digital applications for visual function and reading speed if the subject decides to participate in this portion. This training must occur after completion of all functional tests (NL-BCVA, LL-BCVA). Tests completed using the digital application at select sites (optional) should be completed prior to dilating the eyes but after completion of all functional tests and quality of life measures (NL-BCVA, LL-BCVA, MNREAD or Radner Reading Charts [in select countries], NEI VFQ-25, and FRI). The subject should be instructed to take the electronic device home and to complete the digital application weekly on the same day each week, if possible. The quality of life measures (NEI VFQ-25 and FRI) should be administered by the masked site staff.

Images should be performed including FAF, SD-OCT, OCT-A (select sites), endothelial cell count (select sites), and NIR and sent to the reading center for evaluation.

Study drug or sham injection should be performed by the unmasked physician as described in the MOP and the study eye should be monitored post injection as outlined in [Section 9.15](#). A follow-up phone call should be scheduled with the subject 4 ± 2 days after randomization Day 1 to assess for any AEs.

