5.2. Demographic and Other Baseline Characteristics

Demographic and baseline characteristics will be tabulated using descriptive statistics by treatment group and overall. Tables will be produced for the following analysis sets: ITT, Safety, mITT, Month 12 PP and Month 24 PP (as appropriate), PK, PD, and Genotyping. The following variables will be included in the tables:

The demographic data are:

- Age at screening (years) and in categories
 - < 65
 - 65-<75
 - 75-<85
 - ≥ 85
- Sex
- Race
- Ethnicity
- Geographic Region (United States vs. Rest of World)
- Country
- Weight (kg) at baseline
- Height (cm) at baseline
- Body Mass Index (kg/m^2)
- Tobacco use status (ever, never)

Baseline characteristics will be summarized for both study eye and fellow eye whenever applicable. Baseline characteristics include:

- Study eye laterality (OD, OS)
- Study eye status (better-seeing eye vs. worse-seeing eye, based on NL-BCVA – in the case of ties, study eye status will be classified as the better-seeing eye)
- GA lesion size (mm^2) (assessed by FAF)
- GA lesion size in categories, determined by reading center (as randomized status and actual status):
 - < 7.5 mm^2
 - $\geq 7.5 \text{ mm}^2$
- GA lesion size categories (approximately tertiles based on APL2-303/304 combined data*) – study eye only
- Square root GA lesion size (mm)

- GA lesion location (subfoveal involvement vs. non-subfoveal involvement) (assessed by FAF)
- GA focality (unifocal vs. multifocal) (assessed by FAF)
- Number of areas of atrophy (none, 1, 2-5, 6-10, 11-20, >20, cannot be determined) (assessed from FAF)
- Presence of double-layer sign (DLS) (assessed by SD-OCT)
- Central subfield thickness (CST) (assessed by SD-OCT)
- Presence of macular neovascularization (MNV) (i.e., subclinical CNV) (assessed by Optical Coherence Tomography Angiography (OCT-A))
- Presence of pseudodrusen (assessed by near-infrared reflectance imaging)
- Number of intermediate/large drusen (0-5, 6-10, 11-20, and >20) (assessed by color fundus photography)
- NL-BCVA in ETDRS letters
- NL-BCVA categories (≥ 70 , ≥ 60 - < 70 , ≥ 35 - < 60 , < 35 ETDRS letters)
- NL-BCVA (< 60 vs. ≥ 60 ETDRS letters)
- LL-BCVA in ETDRS letters
- LL-BCVA categories (approximately tertiles based on APL2-303/304 combined data*) – study eye only
- IOP
- LLD in ETDRS letters
- LLD categories (< 20 vs. ≥ 20 ETDRS letters)
- LLD categories (approximately tertiles based on the APL2-303/304 combined data*) – study eye only

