13. DATA HANDLING CONVENTIONS

13.1. General Data Reporting Conventions

Continuous variables will be summarized using the number of non-missing observations (n), mean, SD, median, quartile 1, quartile 3, minimum, and maximum. Geometric mean and CV will be included for PK parameters, where appropriate. Categorical variables will be summarized using frequencies and percentages. Unless stated otherwise, for all percentages, the number of subjects in the analysis population for the treatment group will be the denominator.

Unless otherwise specified, the estimated mean and median for a set of values should be printed out to 1 more decimal place than the original values, and standard deviations should be printed out to 2 more decimal places than the original values. The minimum and maximum should report the same number of decimal places as the original values. Percentages will be displayed with 1 decimal place; except percentages will not be presented when the count is zero and 100% will be presented as an integer.

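### SAP 7.7 reports subclinical CNV on OCT-A as new onset without requiring a negative Day 1 OCT-A

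*SAP*

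**What the plan says.** SAP 2.2.5 lists the endpoint as "Incidence of new onset of subclinical CNV in the study eye". The protocol has the same endpoint as exploratory, with summary statistics only (Protocol 12.7.3).

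The analysis is one bullet under OCT-A in SAP 7.7: "Incidence of subclinical CNV (referred to as MNV in the datasets) determined by OCT-A in eyes without previous CNV reported in the medical history". The bullet goes on to leave out eyes in which CNV was reported as an adverse event, and the result is given by visit.

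Three other places decide which eyes can enter that count:

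- **Eligibility.** Exclusion criterion 3 (Protocol 6.1.2) bars any history of CNV or active CNV in the study eye, including "evidence of neovascularization anywhere based on SD-OCT imaging and/or FA as assessed by the reading center". Protocol 7.1 lists the images that the reading center evaluates for eligibility: FAF, OCT, colour photographs, NIR and FA. OCT-A is not among them.
- **Baseline scan.** Protocol 8.1.2.1 (Visit 2, Day 1) says: "Images should be performed including FAF, SD-OCT, OCT-A (select sites), endothelial cell count (select sites), and NIR and sent to the reading center". The visit schedules (Protocol Appendices A to D) show no OCT-A at screening. They place it on Day 1, at Months 6, 12, 18 and 24, at early termination, and when new active CNV is suspected.
- **Baseline summary.** SAP 5.2 tabulates by treatment group "Presence of macular neovascularization (MNV) (i.e., subclinical CNV) (assessed by Optical Coherence Tomography Angiography (OCT-A". SAP 7.1.1 also lists baseline study-eye MNV for subjects with an exudative AMD event.

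**The concern.** A new-onset rate needs an at-risk set that was free of the condition at baseline. The 7.7 rule builds that set from two records, medical history and adverse events, and ignores the one baseline measurement that detects the condition. A subclinical finding on the Day 1 scan need not appear in either record.

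For study eyes the medical-history filter does little, because exclusion criterion 3 already keeps out eyes with a CNV history.

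The stake is the reading of a safety signal. Protocol 4.1.4 reports new active study-eye exudation in Phase 2 in 25 of 165 pegcetacoplan subjects (15%) and 1 of 81 sham subjects (1%). A natural question for an OCT-A endpoint is whether treatment starts new lesions or whether existing ones begin to leak. A count that mixes lesions present before the first injection with lesions that arise afterwards cannot answer it, and it tends to understate the relative difference between arms.

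**Working it through.** **Text check: can a Day 1-positive eye be counted as incident?**

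1. Can such an eye be randomised? Yes. The CNV exclusion uses SD-OCT and FA, and the eligibility image set has no OCT-A.
2. Does the SAP expect such eyes? Yes. SAP 5.2 provides a baseline row for them.
3. Does 7.7 remove them? Only if the finding is in the medical history or has been reported as an adverse event. No section requires a Day 1 OCT-A reading to be entered as either. SAP 7.4 sends baseline findings to medical history, but only those from the physical examination.
4. Does the SAP use a baseline comparison for similar outcomes? Yes. SAP 7.8 requires a negative baseline result for a treatment-emergent antibody response. Elsewhere in 7.7, haemorrhage, subretinal fluid and cystoid spaces are shifts from baseline. The OCT-A bullet has no such comparison.

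**Size.** The plan states no rate, sample size or power for this endpoint, so there is no figure to reproduce. What follows is an illustration on assumed inputs, none of which is in the documents.

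- p0: prevalence of OCT-A positivity on Day 1, equal in all arms; assumed 2% to 15%.
- s: share of Day 1-positive eyes counted as positive later; assumed 1 (lesions persist).
- I: true cumulative incidence in Day 1-negative eyes; assumed 10% active and 5% sham, a ratio of 2.0.
- No eye leaves the count through the adverse-event exclusion.

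Counted proportion = p0 × s + (1 − p0) × I.

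| p0 | Sham | Active | Ratio | Difference (points) |
|---|---|---|---|---|
| 2% | 0.02 + 0.98 × 0.05 = 6.9% | 0.02 + 0.98 × 0.10 = 11.8% | 1.71 | 4.9 |
| 5% | 0.05 + 0.95 × 0.05 = 9.8% | 0.05 + 0.95 × 0.10 = 14.5% | 1.49 | 4.8 |
| 10% | 0.10 + 0.90 × 0.05 = 14.5% | 0.10 + 0.90 × 0.10 = 19.0% | 1.31 | 4.5 |
| 15% | 0.15 + 0.85 × 0.05 = 19.3% | 0.15 + 0.85 × 0.10 = 23.5% | 1.22 | 4.3 |

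The proportion in each arm rises by p0 × (s − I). The risk difference shrinks only by the factor 1 − p0, here from 5.0 points to between 4.9 and 4.3. The ratio suffers more. At p0 = 5%, baseline disease makes up 0.05 / 0.0975 = 51% of counted sham cases and 0.05 / 0.145 = 34% of counted active cases.

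With s = 0.8 the ratio is 1.75 at p0 = 2% and 1.26 at p0 = 15%, so the pattern does not hang on full persistence. With the baseline requirement in place, the counted proportion is I and the ratio is 2.0.

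**The case against.** The best defence is that the 7.7 bullet is a short output description, to be read with the endpoint name in SAP 2.2.5. That name says new onset, and the bullet says incidence. On this view a programmer would drop Day 1-positive eyes unprompted, and the defect is incomplete wording. The intent is indeed plain. But 7.7 does not leave the at-risk set open: it states an exclusion rule, and that rule, followed as written, keeps these eyes.

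The objections on importance largely stand. The summary is descriptive and limited to select sites. The exudation signal is covered by analyses that do not use this bullet: exudative AMD events with rates per 100 subject-years and Kaplan-Meier estimates (SAP 7.1.1), new CNV on FA, and the reconciliation of suspected with confirmed cases (SAP 7.7). Baseline OCT-A status is tabulated by arm, so a reader can see p0. That table does not show which of those eyes were later counted as incident.

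The objection on size also stands. Study eyes have already passed SD-OCT and FA review, so OCT-A-only prevalence could be low, even below 2%. The bullet refers to each visit and lacks the cumulative wording used for FA, so cumulative counting is itself an assumption.

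A reader might also infer that the denominator is every Safety-set subject, since SAP 13.1 says "the number of subjects in the analysis population for the treatment group will be the denominator", and that the percentage is diluted by sites without the scan. The documents do not establish this. The 13.1 convention yields wherever something else is stated, and 7.7 restricts the summary to a subset of eyes assessed by OCT-A. The number of OCT-A sites is not given either.

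**Conclusion.** The point holds as a defect in the at-risk definition. Followed literally, SAP 7.7 gives a mixture of prevalent and incident subclinical CNV under a new-onset label.

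The direction is clear under stated conditions. The rate rises in an arm whenever Day 1-positive eyes are more likely than Day 1-negative eyes to be positive later. The ratio moves towards 1 if baseline prevalence is balanced, as randomisation should make it on average. At later visits the adverse-event exclusion could remove positive eyes unequally by arm if exudation differs, so balance on Day 1 need not last.

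The amount is not known. The range of about 1.7 down to 1.2 for a true ratio of 2.0 depends on the assumed incidence, prevalence, persistence and cumulative counting. It would be tempting to put the Phase 2 exudation rates into the formula and claim a larger distortion, but those rates concern active exudation, not subclinical lesions. Nothing here touches the primary endpoint, any hypothesis test or the alpha allocation. The change is worth making because the label and the rule disagree on a safety outcome and the correction is cheap.

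**What to change.** Amend the OCT-A bullet in SAP 7.7:

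- Define new onset as MNV absent on a gradable Day 1 OCT-A and present on a later OCT-A in the same eye.
- Keep the existing medical-history and adverse-event exclusions.
- State the denominator: eyes with a gradable, MNV-negative baseline OCT-A and at least one gradable post-baseline OCT-A.
- Report baseline-positive eyes separately by arm.
- Say whether the by-visit figure is cumulative first detection or status at that visit.

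The cost is SAP wording and one derivation. It needs no scans beyond those already scheduled at the OCT-A sites. The drawback is a smaller denominator, because eyes without a gradable negative baseline scan leave the rate.
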